*** A window of 2 days will be allowed when administering ICE chemotherapy**

****If Cycle 3 is to be used for stem cell mobilization, growth factor can be given according to the schedule of stem cell harvest. ie start of growth factor can be >= 48 hrs.**

5.2.6 Patients will receive 3 cycles of ICE every 14 (+/- 2) days, with growth factor support.

5.2.7 Dose modification is allowed as per Table 7.1. ICE treatment should be delayed until ANC > 1,000 /μL, and platelet count > 75,000/μL. Dose delays of ICE >14 days will result in removing the patient from the study.

5.3.8 Repeat imaging studies after 3 cycles.

6.0 TREATMENT EVALUATION:

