6.1 Pre-Treatment Evaluation

Within 30 days (+/- 7 days) of starting therapy

- 6.1.1 Imaging studies (a chest x-ray (CXR), CT scans of the head and neck, chest and abdomen and pelvis, and a PET scan).
- 6.1.2 Bone marrow biopsy, if clinically indicated.
- 6.1.3 Serum HIV test if the patient has risk factors or did not have one within the past 12 months.
- 6.1.4 ECHO/MUGA
- 6.1.5 Medical History Assessment

Within 7 days (+/- 2) of starting therapy

- 6.1.7 CBC with differential, chemistry (albumin, BUN, glucose, ALT/SGPT, AST/SGOT, alkaline phosphatase, LDH, total bilirubin, creatinine, sodium, potassium, calcium, magnesium)
- 6.1.8 EKG
- 6.1.9 Physical examination, vital signs and weight
- 6.1.10 Serum pregnancy test for females of child bearing potential

6.2 Evaluation During The Study:

- Within 7 days of starting each cycle of ICE therapy: physical examination, CBC with differential, SMA and electrolytes.
- Blood (about 2 1/2 teaspoons) will be collected for routine tests.
- Weekly CBC, and electrolytes while on study.
- Toxicity evaluation within 7 days of each ICE therapy.
- Repeat imaging studies after 3 cycles of ICE. (7-13 days after completion of ICE)
- Bone marrow biopsy (if it was positive before starting therapy) and PET scan should be performed to confirm CRs
- EKG 1 (+/- 2 days) per table 6.3
-
- All patients who receive at least one dose of panobinostat will be evaluable for response and toxicity unless the reason for premature termination of the study is reasons other than progression or toxicity (such as poor compliance or patient withdrawal).
- The patient completes the study upon response evaluation with PET scan after 3 cycles of treatment, unless toxicity of grade 3 or greater related to the treatment is ongoing, in which case until it is resolved.

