6.2.1 End-of-Treatment Visit (after completing 3 cycles of ICE) or Withdrawal visit

- Physical exam, including measurement of your weight and vital signs.
- EKG

Patients who benefit from the study drug or the combination, if not eligible for stem cell transplant (SCT), should be allowed to continue on study with the approval of principal investigator (PI) and the attending physician.

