7.1 Criteria for Dosing Modifications

(For Phase II part we suggest the following dose reduction schedule as incorporated in other ongoing studies)

Investigators can use their discretion when making dose-reduction decisions for ICE based on the package insert recommendations unless otherwise specified in the guidelines in Table 7-1 below. In addition Patients should be discontinued from study treatment if they require a dose delay > 14 days from the intended day of the next scheduled dose (for all events other than prolonged QTcF). If a patient cannot be dosed due to prolonged QTcF interval for more than 7 days since last dose, patient should be discontinued from study. All cardiac events should be treated as per the local standard of care and referred to a specialist by the investigator if clinically indicated. Any final decisions concerning any dose modification / interruptions or patient discontinuing study drug permanently should be made by the investigator based on QTcF calculations assessed. Nothing in this protocol or the underlying agreement shall be deemed to restrict or interfere with the independent medical judgment and decision making abilities of the investigator or other M.D. Anderson personnel.

Table 7-1 Criteria for dosing delays, dose-reductions, and re-initiation of treatment due to study drug-related toxicity (excluding QT prolongation) (only applies to Phase II)

Worst Toxicity CTCAE Grade**** unless otherwise specified (Value)		Dose Modification Guidelines At any time during a cycle of therapy (including intended day of dosing)*
HEMATOLOGICAL TOXICITIES		
Thrombocytopenia	Grade 4 (< 25 x 10 ⁹ /L)	Temporarily discontinue panobinostat dosing until resolved to ≤ grade 2, or baseline, then: 
 restart panobinostat reduced by one dose level If event recurs, hold drug and resume at next lower dose level*
Neutropenia (ANC)	Grade 4 (ANC < 0.5 x 10 ⁹ /L)	Temporarily discontinue panobinostat dosing until resolved to ≤ grade 3, or baseline, then: 
 Restart panobinostat reduced by one dose level If event recurs, hold drug and resume at next lower dose level*
	Febrile neutropenia (ANC < 1.0 x 10 ⁹ /L, fever ≥ 38.5°C)	Temporarily discontinue panobinostat dosing until fever resolved and ANC ≤ grade 2, then restart panobinostat reduced by one dose level
NON-HEMATOLOGICAL TOXICITIES		
CARDIAC		
Cardiac - Prolonged QT interval**		Please refer to Section 7.2
GASTROINTESTINAL		

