9.2 Termination of Treatment and/or Study Participation

Patients will be informed that they have the right to withdraw from the study at any time for any reason, without prejudice to their medical care. The investigator also has the right to withdraw patients from the study for any of the following reasons:

- Intercurrent illness
- Occurrence of an unacceptable adverse event
- A treatment cycle delay of ICE > 14 days
- Patient request
- Protocol violations
- Non-compliance
- Administrative reasons
- Failure to return for follow-up
- General or specific changes in the patient's condition unacceptable for further treatment in the judgment of the investigator
- Progressive disease.

At the time of withdrawal, all study procedures outlined for the End of Study visit should be completed. The primary reason for a patient's withdrawal from the study is to be recorded in the source documents.

All AEs will be followed for 30 days post last dose of study drug and recorded in database

10.0 STATISTICAL CONSIDERATION:

Phase I design:

The objective of the phase I portion is to determine the maximum tolerated dose (MTD) of Panobinostat in combination with ICE. The dose level for ICE is fixed. There are three predefined dose levels for Panobinostat.

Dose Level	Panobinostat (mg, orally) Monday-Wednesday-Friday
-1	10
0	20
1	30

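### Phase II patients whose ICE is delayed more than 14 days leave the study with no response scan scheduled, and the only evaluability rule is tied to panobinostat, so early stoppers have no common CR rule across arms

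*Combined protocol and SAP*

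**What the plan says.** **Removal for delay.** Three sections deal with an ICE delay of more than 14 days.
- Section 5.2.7 is mandatory: "Dose delays of ICE >14 days will result in removing the patient from the study".
- Section 7.1 speaks of treatment only: "Patients should be discontinued from study treatment if they require a dose delay > 14 days".
- Section 9.2 makes it discretionary. Under "The investigator also has the right to withdraw patients from the study for any of the following reasons" it lists "A treatment cycle delay of ICE > 14 days".

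**Imaging.** Sections 5.2 (last item) and 6.2 repeat imaging after 3 cycles, with 6.2 placing it 7 to 13 days after ICE ends. Section 10 evaluates response after 3 doses of ICE.

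**Withdrawal procedures.** Section 6.2.1 is headed "End-of-Treatment Visit (after completing 3 cycles of ICE) or Withdrawal visit" and lists a physical exam and an EKG. Section 9.2 adds: "At the time of withdrawal, all study procedures outlined for the End of Study visit should be completed". No visit is defined under that name.

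**Evaluability.** Section 6.2 states: "All patients who receive at least one dose of panobinostat will be evaluable for response and toxicity". It then excepts premature termination for reasons other than progression or toxicity, giving poor compliance and patient withdrawal as examples.

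**Analysis.** Section 10 estimates the CR rate with a 95% CI in each arm. It bases each randomisation on the data entered in the trial website. For phase II it names no analysis population and gives no rule for a patient without a response assessment. The replacement rule in 5.1.7 concerns phase I cohorts.

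**The concern.** A patient who stops for toxicity after one or two cycles never reaches the only scheduled response scan. The sections on withdrawal do not ask for one.

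What happens to that patient in the analysis is not settled. In the panobinostat arm, 6.2 makes a toxicity exit evaluable but does not say how to score it without a scan. In the ICE arm no rule applies at all. Patients who stop for non-compliance or withdrawal are excluded after randomisation in the panobinostat arm, and the ICE arm is again not addressed.

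In a fixed-allocation trial a later sensitivity analysis could expose this. Here the CR data as entered set the allocation probability, the 0.975/0.025 early rules and the final 0.95 rule, so inconsistent entry affects the trial while it runs. Exits may also differ by arm: the QTcF stopping rules in 7.2 and Table 7-2 can act only on patients taking panobinostat.

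**Working it through.** **1. Text side by side.** An ICE delay over 14 days leads to removal (5.2.7), stopping treatment (7.1) or possible withdrawal (9.2). A removed patient has no scan under 6.2.1. The PET that 6.2 ties to completing the study comes after 3 cycles, which this patient has not had. The evaluability rule depends on a panobinostat dose, which no ICE-arm patient receives.

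**2. Reproducing the plan.** Inputs from section 10: Beta(0.5, 0.5) priors; first 20 patients 10:10; then allocation by Pr(πi > πj | data); early rules 0.975/0.025; final rule 0.95; maximum 70; 3 patients per month; response at 2 months. With every patient assessed (200,000 simulated trials, Monte Carlo SE about 0.001):

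| True CR, ICE / panobinostat+ICE | Quantity | Plan | Recomputed |
|---|---|---|---|
| 0.50 / 0.50 | Pr(select ICE) | 0.117 | 0.124 |
| 0.50 / 0.50 | Pr(select panobinostat+ICE) | 0.122 | 0.124 |
| 0.50 / 0.70 | Pr(select panobinostat+ICE) | 0.573 | 0.584 |

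The plan's table is consistent with every patient having an observed outcome.

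**3. Illustration: exits left out of both arms.** Exit rates and CR in exits are assumptions. Let p be CR among all randomised, q the exit proportion and e the CR in exits. CR among those assessed is c = (p − q·e)/(1 − q). Patients left out count towards 70 but add no data. With p = 0.50 in both arms and e = 0:

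| Exits, ICE v panobinostat+ICE | c, ICE | c, panobinostat+ICE | False selection of panobinostat+ICE |
|---|---|---|---|
| 5% v 5% | 0.50/0.95 = 0.526 | 0.526 | 0.124 |
| 5% v 10% | 0.526 | 0.50/0.90 = 0.556 | 0.165 |
| 5% v 15% | 0.526 | 0.50/0.85 = 0.588 | 0.222 |

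**4. Dependence on CR in exits.** At 5% v 15%, in a separate run of 15,000 trials (SE about 0.003):
- e = 0: false selection of panobinostat+ICE 0.220.
- e = 0.25: c = 0.4875/0.95 = 0.513 v 0.4625/0.85 = 0.544; false selection 0.167.
- e = 0.50: c = 0.50 in both arms; false selection 0.134 (0.129 in another run of 5,000 trials), about a point from the no-exit value.

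Leaving patients out therefore biases the result only if exits respond less, or more, often than completers.

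**5. The opposite direction.** Suppose ICE exits are left out and panobinostat exits are scored non-CR, with 10% exits in each arm and e = 0. ICE is then falsely selected in 0.211 and panobinostat+ICE in 0.070. This needs no difference in exit rates, only different handling by arm.

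**6. Why the scan matters as well as the counting rule.** Suppose exits would show CR at 0.25 if scanned, at 5% v 15%. Scoring them unscanned as non-CR records 0.50 − 0.05 × 0.25 = 0.4875 v 0.50 − 0.15 × 0.25 = 0.4625. A true tie then selects ICE in 0.159 and panobinostat+ICE in 0.095.

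**7. Timing.** On schedule, cycle 3 starts on day 29 and ICE ends on day 31, so the scan falls on days 38 to 44. A delay of more than 14 days is reached on day 30 for cycle 2 (due day 15) and on day 44 for cycle 3 (due day 29).

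**The case against.** The strongest reply is that much of this is loose wording. Section 9.1 also removes transplant-eligible responders from the study, and their CR plainly counts, so removal need not mean lost data. Section 7.1 speaks only of stopping treatment. Section 6.2 has patients complete the study at the PET scan, so the End of Study procedures in 9.2 might be read to include it. This stands in part: some of the problem is inconsistency between sections. It does not supply the scan, because 6.2.1 names the withdrawal visit and lists its contents, and the PET in 6.2 follows 3 cycles.

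The figures are also open to challenge, and rightly.
- The exit rates have no source.
- Leaving panobinostat toxicity exits out goes against 6.2, which calls them evaluable. That case arises only if unscanned patients are never entered.
- Step 5 is a hybrid. Section 6.2 names no ICE patient, completer or exit, so dropping only ICE exits is not its literal meaning.

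A reader might infer that panobinostat patients will exit more often and that the trial will therefore favour one arm. The documents do not support that. Section 2.5 reports ICE delayed in all 21 schedule A patients, but by one week, within the limit, and Table 5.2 gives schedule B for phase II. Table 1-3 shows QTcF above 480 ms in 4 of 102 patients at 20 mg and 0 of 9 at 30 mg, in other studies; this trial excludes screening QTc above 450 msec. Neither is an exit rate.

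Finally, scoring unassessed patients as non-CR is a choice. If exits are unrelated to response, at 5% v 15% to 25% and without added scans, it lowers selection of panobinostat+ICE at 0.50 v 0.70 from 0.591 to between 0.351 and 0.203. That is a reason to add the scan, not to leave the rule unstated.

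**Conclusion.** The concern holds in this form: as written, the plan can lose the primary outcome for early stoppers, it allows exclusions after randomisation, and its one evaluability rule does not serve the ICE arm. This goes beyond missing detail, because a stated rule depends on the experimental drug in a design where CR steers allocation, stopping and selection. It should be corrected before phase II randomisation.

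The documents establish neither the direction nor the size of any bias. The rise from about 0.12 to about 0.165 assumes exits of 5% v 10%, all non-CR and all left out. It moves towards nil as CR in exits approaches CR in completers, it disappears with equal exits left out of both arms, and it can reverse under different handling by arm. The simulated figures show that the handling rule matters; they do not predict what this trial would do.

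**What to change.** For randomised phase II patients:
1. In 5.2.7, 7.1, 7.2, Table 7-2 and 9.2, replace removal or discontinuation from the study with discontinuation of study treatment. In 9.2, leave patient request and failure to return as they are. Keep every stopping threshold unchanged.
2. Add the planned response PET/CT to 6.2.1 for anyone who stops after at least one ICE cycle, unless consent is withdrawn or progression is documented. Do it at the post-cycle-3 time, or promptly if that time has passed. Always do it before new anticancer therapy, since 7.3 requires withdrawal before such therapy starts.
3. State that 6.2.1 is the End of Study visit meant in 9.2.
4. Replace the 6.2 evaluability rule with one rule for both arms: all randomised patients count for CR, those unassessed count as non-CR, and they are entered that way in the randomisation system.

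The cost is protocol wording and a few scans. There are two downsides. A scan after shortened treatment may show fewer CRs than one after 3 cycles. Patients who stop before any ICE, such as QTcF exits at day -6 or -2, count against their arm.

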6.1 Pre-Treatment Evaluation

Within 30 days (+/- 7 days) of starting therapy

- 6.1.1 Imaging studies (a chest x-ray (CXR), CT scans of the head and neck, chest and abdomen and pelvis, and a PET scan).
- 6.1.2 Bone marrow biopsy, if clinically indicated.
- 6.1.3 Serum HIV test if the patient has risk factors or did not have one within the past 12 months.
- 6.1.4 ECHO/MUGA
- 6.1.5 Medical History Assessment

Within 7 days (+/- 2) of starting therapy

- 6.1.7 CBC with differential, chemistry (albumin, BUN, glucose, ALT/SGPT, AST/SGOT, alkaline phosphatase, LDH, total bilirubin, creatinine, sodium, potassium, calcium, magnesium)
- 6.1.8 EKG
- 6.1.9 Physical examination, vital signs and weight
- 6.1.10 Serum pregnancy test for females of child bearing potential

6.2 Evaluation During The Study:

- Within 7 days of starting each cycle of ICE therapy: physical examination, CBC with differential, SMA and electrolytes.
- Blood (about 2 1/2 teaspoons) will be collected for routine tests.
- Weekly CBC, and electrolytes while on study.
- Toxicity evaluation within 7 days of each ICE therapy.
- Repeat imaging studies after 3 cycles of ICE. (7-13 days after completion of ICE)
- Bone marrow biopsy (if it was positive before starting therapy) and PET scan should be performed to confirm CRs
- EKG 1 (+/- 2 days) per table 6.3
-
- All patients who receive at least one dose of panobinostat will be evaluable for response and toxicity unless the reason for premature termination of the study is reasons other than progression or toxicity (such as poor compliance or patient withdrawal).
- The patient completes the study upon response evaluation with PET scan after 3 cycles of treatment, unless toxicity of grade 3 or greater related to the treatment is ongoing, in which case until it is resolved.

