5.2 Phase-II

- 5.2.1 The starting dose of panobinostat will be based on the data generated from the phase-I portion of this study.
- 5.2.2 Patients will be randomized by MDACC to arm 1 (ICE) or arm 2 (Panobinostat + ICE) as shown in Table 5.2.
- 5.2.3 For cycle 1 of the panobinostat arm, panobinostat will be given on day -6. (See Fig1)
- 5.2.4 Cycle 3 of both arms will be ICE alone (to minimize any potential effect on stem cell collection)

Table 5.1
Schedule A

Day of cycle	HDACi	Chemotherapy(ICE)			Growth factor
-6	Panobinostat				
-5					
-4	Panobinostat				
-3					
-2	Panobinostat				
-1					
0					
1	Panobinostat	Ifex/Mesna	Carboplatin	Etoposide	
2				Etoposide	
3	Panobinostat			Etoposide	
4					start growth factor support
5	Panobinostat				
6					
7					
8	Panobinostat				
9					
10	Panobinostat				
11					
12	Panobinostat				
13					
14					

Table 5.1.1 Dosing Schedule B

Day of cycle	HDACi	Chemotherapy(ICE)			Growth factor
-6	Panobinostat				
-5					
-4	Panobinostat				
-3					
-2	Panobinostat				
-1					
0					
1	Panobinostat	Ifex/Mesna	Carboplatin	Etoposide	
2				Etoposide	
3	Panobinostat			Etoposide	
4					start growth factor support
5	Panobinostat				
6					
7					
8					
9					
10					
11					
12					
13					
14					

5.2.5 The doses of each drug are shown in the following table 5.2.

Table 5.2. Doses of ICE vs panobinostat + ICE				
	Arm 1 (ICE)	Arm 2 (Panobinostat + ICE) Schedule B		
Day	Drug	Drug	Dose	Infusion time
Starting day -6 and given 3 times per week during cycles 1 and 2		PANOBINOSTAT (LBH589)	MTD determined by phase I	Oral
1	Ifosfamide + Mesna	Ifosfamide + Mesna	5 grams/m ² equal dose of each	IV continuous infusion over 24 hours
2	Mesna	Mesna	2 grams/m ²	IV continuous infusion over 12 hours
1	Carboplatin	Carboplatin	standard dose (target AUC=5mg/ml/min)	IV over 1 hr
1, 2, 3	Etoposide	Etoposide	100 mg/m ² /day	IV over 2 hours
4**(12-48 hrs after completion of ICE)	growth factor support	growth factor support	Standard dose	

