7.2 Dose modifications for prolonged QTcF interval

All cardiac events should be treated as per the local standard of care and referred to a specialist if clinically indicated. Any final decisions concerning dose modifications or permanently discontinuing the patient from study drug due to QTcF prolongation will be based on the assessment of the Investigator. Any plan to deviate from these guidelines should be previously discussed and agreed upon by the investigator. If a patient cannot be dosed due to prolonged QTcF for more than 7 days since last dose, patient should be discontinued from study.

Table 7-2 Criteria for dosing delays, dose-reductions, and re-initiation of treatment due to study drug-related QTcF abnormalities

ECGs to be performed at specified time point	Abnormality Noted	Dose Modification Guideline - At any time during a cycle of therapy (including intended day of dosing)
Cycle 1 dose modifications		
Pre-dose for each cycle on day 1 for cycle 2 and 3 and for day -6 and -2 on cycle 1 only:	If Day 1 for cycles 2 and 3 and day -6 and -2 for cycle 1 only: A single ECG obtained shows QTcF > 460 msec	
Check and correct the patient's serum potassium, magnesium, calcium and phosphorus immediately, as well as evaluate con-meds.
 
Notify Investigator immediately for prompt review.
 
If abnormality noted on Day 1 of Cycle 2 and 3 and day -6 and -2 for cycle 1 only:
 
Delay dose at least 3 days and repeat pre-dose ECG. If the pre-dose ECG:
 
Do not meet criteria again, discontinue patient from study.
 
Do meet criteria for dosing; administer study drug treatment at.
 
Do meet pre-dose ECG criteria for dosing and QT prolongation determined to be related to study drug, resume study drug treatment with a dose reduction of 10 mg. If however, it was determined that the QT prolongation was secondary to electrolyte abnormalities or con-meds, continue at the same dose level. Repeat ECGs - pre-dose (x3), 3-hours post-dose (x3), and 6-hours post-dose (x3) on the next scheduled dosing day after the reduced dose is given.*

	A single ECG obtained shows QTcF >480 msec to \geq 500 msec	
Check and correct the patient's serum potassium, magnesium, calcium and phosphorus immediately.
 
Notify Investigator immediately for prompt review. Discontinue patient from study therapy

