The phase II part of this study is to evaluate ICE only and Panobinostat +ICE in treating patients with classical Hodgkin lymphoma. The primary outcome is complete remission (CR). The estimated accrual rate is 3 patients per month. A maximum of 70 patients will be accrued. Patients will be evaluated for response after receiving 3 doses of ICE (3 cycles). The patients will be randomized between ICE and Panobinostat + ICE arms using a Bayesian adaptive algorithm. The dose level for Panobinostat will be the dose level determined after the phase I expansion cohort. In general, the trial will proceed as follows: The initial 20 patients will be randomized fairly with probability of 0.50 each between the two arms, so that the number of patients in each arm is equal at the start of the trial. Thereafter, as the trial proceeds patients will be randomized to the two groups with unequal probabilities in favor of the treatment that, on average, yields better response rate. Consequently, each successive patient is more likely to receive the treatment with a better response rate, on average. The details of the adaptive randomization scheme are as follows:

Denote the response rate at each of the two treatment arms by $\{\pi_1, \pi_2\}$ (1 for ICE, 2 for Panobinostat+ICE). Based on the currently available data, we assume the prior distribution for the complete response rate at 3 cycles (2 months) is $\pi_i \sim \text{Beta}(0.5, 0.5)$ where $i=1, 2$. The resulting prior mean is 0.5. After the initial first 20 patients being randomized to two treatment groups with an equal probability, each new patient will be randomized to receive treatment i with probability $\rho_i = \text{prob}(\pi_i > \pi_j, j \neq i | \text{Data})$, $i, j=1,2$. If one of these two randomization probabilities falls below 0.025 then that arm will be dropped. On the other hand, if one of the two randomization probabilities exceeds 0.975 then the trial will be terminated and that treatment arm will be selected. If the trial does not stop early and the maximum 70 patients are accrued, a treatment is selected as being “better” if the probability that one treatment’s response rate is larger than the other’s response rate exceeds 0.95.

The Table below summarizes operating characteristics of the Bayesian adaptive randomization algorithm after we simulated 5,000 trials. We assume that the number of patients accrue per month is 3.

		Treatment arms	
		ICE	Panobinostat-ICE

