Scenario 1:	True Prob(Complete Remission)	0.50	0.50
	Average # Patients Treated	31.2 (10, 55)	30.8 (10, 54)
	Pr(Selected)	0.117	0.122
	Pr(Selected Early)	0.0998	0.105
	Pr(Dropped Early)	0.108	0.102
	Average Length (months) to the last patient's response evaluation		23.1
Scenario 2:	True Prob(Complete Remission)	0.50	0.70
	Average # Patients Treated	19.1 (10, 45)	32.8 (10, 55)
	Pr(Selected)	0.0098	0.573
	Pr(Selected Early)	0.0096	0.49
	Pr(Dropped Early)	0.513	0.0096
	Average Length (months) to the last patient's response evaluation		18.8
Scenario 3:	True Prob(Complete Remission)	0.50	0.80
	Average # Patients Treated	14.2 (10, 31)	25.7 (10, 55)
	Pr(Selected)	0.0022	0.859
	Pr(Selected Early)	0.0022	0.781
	Pr(Dropped Early)	0.808	0.0022
	Average Length (months) to the last patient's response evaluation		14
Scenario 4:	True Prob(Complete Remission)	0.60	0.80
	Average # Patients Treated	18 (10, 42)	31.7 (10, 56)
	Pr(Selected)	0.0068	0.638
	Pr(Selected Early)	0.0068	0.556
	Pr(Dropped Early)	0.576	0.0068
	Average Length (months) to the last patient's response evaluation		17.9

The trial will be conducted using the Clinical Trial Conduct website (<https://biostatistics.mdanderson.org/ClinicalTrialConduct>) developed in University of Texas MD Anderson Cancer Center Department of Biostatistics. Through the web interface, the users can randomize patients and update last evaluation date and current patient status. When a patient is randomized, the calculations are based on all available data entered into the website. The results of the randomization are displayed to the screen for the user to view. All data will be stored in a secure SQL server database. For safety, in addition to the MDACC DSMB annual monitoring, the team including the PI, one or 2 other select investigators, and the statistician will meet at every 10 patients for the Panobinostat +ICE arm to review the toxicity data.

Analysis Plans

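### The only evaluability rule is tied to taking panobinostat and is not limited to phase I, so as written it allows post-randomisation exclusions in one phase II arm only

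*Combined protocol and SAP*

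**What the plan says.** **Evaluability.** Section 6.2 (Evaluation During The Study) states: "All patients who receive at least one dose of panobinostat will be evaluable for response and toxicity unless the reason for premature termination" falls under "reasons other than progression or toxicity (such as poor compliance or patient withdrawal" and the like. Nothing in that section restricts the sentence to phase I. No other section defines who is evaluable for response.

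**Phase II comparison.** Section 5.2.2: "Patients will be randomized by MDACC to arm 1 (ICE) or arm 2 (Panobinostat + ICE", so one arm never takes panobinostat. Section 10.0, Phase II, makes CR the primary outcome, caps accrual at 70 and says: "Patients will be evaluated for response after receiving 3 doses of ICE (3 cycles". For the adaptive randomisation, "the calculations are based on all available data entered into the website". The Analysis Plans part of Section 10.0 promises a CR rate with a 95% CI per arm, but states no denominator and no treatment of a patient without a response.

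**Routes to a missing response.** Section 5.2.7: "Dose delays of ICE >14 days will result in removing the patient from the study". Section 7.2: "If a patient cannot be dosed due to prolonged QTcF for more than 7 days since last dose, patient should be discontinued from study". Section 9.2 lists further grounds for withdrawal, including patient request and non-compliance.

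**Assessment on leaving.** Section 6.2 schedules response imaging after three cycles. Section 6.2.1, which also serves as the withdrawal visit, lists "Physical exam, including measurement of your weight and vital signs" and an EKG. Section 9.2 asks that the procedures of an End of Study visit be completed at withdrawal, but no section has that name.

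**Replacement.** Section 5.1.7 replaces some patients, in phase I cohorts only.

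**The concern.** The sentence in Section 6.2 suits a single-arm phase I, where everyone is meant to take panobinostat. In a randomised comparison it makes membership of the response set depend on something that happens after randomisation and can happen in one arm only. A panobinostat-ICE patient who withdraws or complies poorly may leave the denominator; an ICE patient who does the same is not mentioned. A patient randomised to panobinostat-ICE but never dosed is also uncovered. That is a real possibility: Table 7-2 allows discontinuation on ECGs taken before the first dose on day -6.

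The CR count and the number of patients per arm feed three decisions: each allocation after patient 20, the 0.025/0.975 early bounds and the 0.95 final bound. No blinding is described for phase II. If the denominator is not fixed in advance, it will be settled case by case while arm and outcome are known.

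**Working it through.** **1. Inputs from Section 10.0.** Accrual 3 per month; outcome at 2 months; maximum 70; first 20 patients split equally (taken as 10:10); Beta(0.5, 0.5) priors; bounds 0.025/0.975 early and 0.95 at the end. With x CRs among n counted patients in arm i, the posterior is Beta(0.5 + x, 0.5 + n − x). The allocation probability is ρ_i = P(π_i > π_j | data). The early bounds were checked before each randomisation after patient 20, with 60,000 simulated trials per case (Monte Carlo 95% error about ±0.003 to 0.004).

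**2. Reproducing the plan's table, with every patient assessed.**

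| True CR, ICE / panobinostat-ICE | Pr(panobinostat-ICE selected), plan | Reproduced |
|---|---|---|
| 0.50 / 0.50 | 0.122 | 0.120 |
| 0.50 / 0.70 | 0.573 | 0.577 |
| 0.50 / 0.80 | 0.859 | 0.841 |
| 0.60 / 0.80 | 0.638 | 0.625 |

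In the first scenario ICE is selected with probability 0.118 (plan 0.117), and mean patients per arm are 31.0 / 31.1 (plan 31.2 / 30.8). The largest gap in the table is 0.859 − 0.841 = 0.018. The plan does not describe every detail of its simulator, so the match is close but not exact. It shows that the stated figures correspond to a trial with no unassessed patients.

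**3. Assumed loss.** The documents give no rate, so 3%, 5% and 10% are assumptions. On the plan's average of 30.8 panobinostat-ICE patients, 5% is 30.8 × 0.05 = 1.5 patients and 10% is 3.1.

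**4. Effect of panobinostat-only exclusion on the observed CR rate.** With overall CR p, excluded share l and CR among the excluded c:

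CR among those kept = (p − l × c) / (1 − l)

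At p = 0.50:
- c = 0, l = 0.05: 0.50 / 0.95 = 0.526
- c = 0, l = 0.10: 0.50 / 0.90 = 0.556
- c = 0.25, l = 0.05: (0.50 − 0.0125) / 0.95 = 0.513
- c = 0.25, l = 0.10: (0.50 − 0.025) / 0.90 = 0.528
- c = 0.50, any l: 0.50, no shift

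**5. False selection of panobinostat-ICE, true CR 0.50 in both arms.** No loss gives 0.120. With exclusions from the panobinostat-ICE arm only:

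| CR among the excluded | 3% | 5% | 10% |
|---|---|---|---|
| 0.50 (unrelated to response) | – | 0.122 | 0.122 |
| 0.25 | – | 0.140 | 0.160 |
| 0 (upper bound) | 0.141 | 0.156 | 0.206 |

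Two repeat runs of 15,000 trials put the 10% upper bound at 0.199 and 0.203.

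**6. One rule for both arms, equal 10% loss.** Coded non-CR: 0.120. Excluded: 0.121 to 0.123. With equal loss, either common rule keeps the error where the plan put it.

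**The case against.** **Section 6.2 drops only some patients.** Those who stop for progression, the clearest non-CRs, remain evaluable. So do those who stop for toxicity, which would include QTcF discontinuations and ICE delays caused by low counts. Only compliance, withdrawal and similar losses are removed, and no text says such patients are all non-responders. If they resemble the rest, the effect is nil (0.122 against 0.120). This stands. The bottom row of the table in step 5 of the working is therefore an upper bound, not an expected value.

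**Non-CR is already the natural coding for some patients.** Section 6.2 wants PET to confirm a CR, and Section 8.0 defines CR by imaging criteria. A dosed patient who stops for toxicity or progression and has no confirming scan does not meet that definition. This also stands, although the documents do not state the coding. The stable-disease category in Section 8.0 does not state it either: it is a response category with PET/CT criteria, not a missing-data rule.

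**Imaging at withdrawal may be intended.** Section 9.2 points to an End of Study visit, and Section 6.2 ties study completion to a PET-based evaluation. A reader might infer from Section 6.2.1 that patients who leave early are never imaged. The documents do not support so firm a reading; they are unclear.

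**Opposite conventions in the two arms.** A reader might also infer that panobinostat patients would be dropped while unassessed ICE patients are coded non-CR, which gives 0.155 at 5% and 0.196 at 10% equal loss unrelated to response. Nothing in the documents codes ICE patients that way. Silence on ICE is not a contrary rule, so these figures are hypothetical.

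**The sentence may be a phase I leftover.** It reads like one. If so, phase II has no rule at all, and the remedy is the same.

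**Conclusion.** The point holds in this form: the documents' only evaluability rule depends on panobinostat intake, is not limited to phase I, and is not overridden in Section 10.0. As written, it allows post-randomisation exclusions from the panobinostat-ICE arm alone. It leaves ICE patients and never-dosed panobinostat-ICE patients without a rule.

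Its size depends on assumed loss rates and on how the excluded patients would have responded. False selection of panobinostat-ICE ranges from no change (about 0.12), through 0.14 to 0.16 at a CR of 0.25 among 5% to 10% excluded, to bounds of about 0.16 and 0.20–0.21 if none of them is in CR. It would be going too far to say that the trial is biased towards panobinostat-ICE. The text permits bias but does not show that any exclusions would occur or be related to response. This should be fixed before phase II begins; it does not invalidate the design.

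**What to change.** 1. Limit the evaluability sentence in Section 6.2 to phase I.
2. Add to Section 10.0 one rule for both phase II arms, for example: *All randomised patients are analysed in the arm assigned, for the adaptive randomisation, the stopping bounds and the final CR estimate. A patient who leaves the study without a post-cycle-3 response assessment counts as not in CR. Patients still awaiting that assessment enter the interim counts once assessed.*
3. Add a sensitivity analysis that applies the same exclusion rule in both arms, and report unassessed patients by arm with reasons.
4. Reconcile Sections 6.2.1 and 9.2 on which assessments are due at withdrawal.
5. Rerun the operating-characteristics table with an assumed unassessed share.

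**Cost.** About a paragraph of text and a rerun of the simulation. Reported CR rates fall slightly: with 10% unassessed regardless of response, a true 0.50 is observed as 0.50 × 0.90 = 0.45. Pr(panobinostat-ICE selected) changes as follows when both arms are coded non-CR:

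| True CR | No loss | 5% | 10% |
|---|---|---|---|
| 0.50 / 0.70 | 0.577 | 0.541 | 0.508 |
| 0.50 / 0.80 | 0.841 | 0.800 | 0.755 |
| 0.60 / 0.80 | 0.625 | 0.577 | 0.531 |

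Excluding the 10% from both arms instead gives 0.548 at 0.50 / 0.70.

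Non-CR coding also penalises an arm with more loss unrelated to response. With 10% loss on panobinostat-ICE and 5% on ICE, selection at 0.50 / 0.70 falls to 0.441, and at 0.50 / 0.50 false selection of ICE rises from 0.118 to 0.154. If the lost patients are truly non-CR, excluding them from both arms at those rates gives false selection of panobinostat-ICE of 0.162, against 0.120 when coded non-CR. Neither rule is best in every case, which is why the sensitivity analysis is needed. The essential requirement is a single rule, fixed in advance, for both arms.
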